#### 6.6.4 Missing and incomplete laboratory reference ranges

Incomplete (one-sided) laboratory reference ranges are imputed according to BI standards (see “Handling of incomplete reference ranges”) ([14](#)).

In case of serum N-terminal cross-linked telopeptide (NTx), central lab reference range was not included in the data transfer as it was based on the Tanner stage score. The Tanner stage score was unknown to the central lab. This missing central lab reference range will be incorporated in the Analysis Data Model (ADaM) dataset based on the Tanner stage score according to the central lab reference ranges ([15](#)).

#### 6.7 BASELINE, TIME WINDOW, AND CALCULATED VISITS

The term “baseline” refers to the following definitions according to the individual analysis period.

- *Study baseline*: Last observed measurement prior to administration of any initially randomised study medication at Day 1.
- *Titration baseline*: Last observed measurement prior to administration of the re-randomised study medication for the initial empagliflozin patients at Week 14. If last observed measurement is after rescue medication then there is no titration baseline for OC analysis.
- *Safety extension baseline*: Last observed measurement prior to administration of the re-randomised study medication for the initial placebo patients at Week 26.

Note: On or prior to date of randomisation will be used, instead of prior to date of drug administration, for randomised patients who have not taken any blinded study drug.

Both date and time of administration of the randomised study medication are expected to be recorded at Day 1, Week 14 and Week 26. In the determination of baseline for a parameter, if the parameter of interest:

- is collected with date and time: both date and time are used in the calculation of ‘last observed measurement prior to administration’. If the dates and times are equal, the parameter will be determined to be prior to administration.

- is collected with only date: the dates are equal, the parameter will be determined to be prior to administration.

The exception to this rule, is HbA1c, whereby even though time of sample is collected, it will be handled as if it was collected only with date.

Measurements taken after the first intake of randomised study drug will be considered on-treatment values if they have been obtained up to the end of the endpoint specific follow-up period as defined in [Table 6.7: 1](#).

Table 6.7: 1 Endpoint specific follow-up period for the assignment to treatment phase

Endpoint	Last day of assignment to treatment phase (days after study drug stop date)
Efficacy	
HbA1c	7
FPG	1
Body weight	1
BMI z-score	1
Blood pressure (systolic, diastolic)	1
UACR	7
Safety	
Adverse events	7
AESI Hepatic injury 	30
AESI Lower limb amputation	End of study
Safety laboratory measurements	7
AST/ALT/TBILI 	30
Pulse rate	1
C-peptide	1
Tanner staging	1

[1] Refers to a specific safety analysis including all hepatic injuries with an onset date up to 30 days after the study treatment stop.

[2] Refers to a specific safety analysis on elevated liver enzymes, for which events with an onset date up to 30 days after the study treatment stop will be included in the analysis. See [Section 7.8.2.2](#).

Measurements taken after the last intake of study drug and end of the endpoint specific follow-up period will be considered post-treatment values. In efficacy analyses, the words off-treatment and post-treatment are used synonymously.

Efficacy and safety measurements will be assigned to visits based on time windows around the planned visit dates. These time windows are defined based on the planned number of days after the date of first administration of study drug (see [Table 6.7: 2](#)).

Table 6.7: 2 Time windows for efficacy and safety measurements at scheduled visits after randomisation

Visit number	Visit label	Planned days on treatment	Planned days after randomisation	Time window (actual days on treatment)	
				Start	End A
2	Baseline	1	0 C	NA	1 B
3	Week 4	29	28	2	56
4A	Week 12	85	84	57	91
4B	Week 14	99	98	92	140 B
5	Week 26	183	182	141	Max(Day 141, Visit 5 drug intake date, Min(Day 210, Visit 6 date – 1 day))
6	Week 30	211	210	Max(Day 141, Visit 5 drug intake date, Min(Day 210, Visit 6 date – 1 day)) + 1 day	225
7	Week 42	295	294	226	329
8	Week 52 / EoT	365	364	330	Study drug stop date + X days

A In case of premature discontinuation of the study drug an early EoT visit has to be performed. Measurements from the early EoT visit will be assigned to the appropriate visit according to the table. Patients will then be asked to continue in the study according to the visit schedule. Post-treatment measurements will be assigned to visits in the same manner.

B Only values taken prior to the start of treatment at Day 1, Week 14 and Week 26, with randomised study drug can be considered study baseline, titration baseline and safety extension baseline accordingly. Time windows will be used for assignment of measurements to scheduled visits.

C Reference day (day 0) is day of randomisation

The mid-point between two visits defines the end of a time window, with the midpoint being included in the time window of the preceding visit. The end of the time window of the last on-treatment visit (EoT) is endpoint dependent (cf. [Table 6.7: 1](#)). As endpoints are planned to be measured according to different visit schedules, this midpoint algorithm will be applied and the time windows modified accordingly.

Only one observation per time window will be selected for analysis. If there are multiple values within a time-window, the value closest to the CTP planned visit day will be selected. If there are two observations which have the same difference in days to the planned day or if there are two observations on the same day, the earliest value will be used. If an observation

is available on the last day of treatment, this observation will be preferably selected over any later observation that is still within the time window. For the Week 26 primary analysis, this is applicable if study drug is stopped during the time window of the Week 26 visit.

In addition to the HbA1c values, both National Glycohemoglobin Standardization Program (NGSP) certified and non-NGSP certified HbA1c values, will be used in HbA1c endpoints analyses, given that they are in the same unit. The order of preference for the laboratory values are: (1) NGSP certified central laboratory values, (2) NGSP certified local laboratory values and (3) non-NGSP certified local laboratory values. If a visit window includes a NGSP certified local laboratory value as well as a non-NGSP certified local laboratory value (either both being on- or post-treatment), then the NGSP certified value will be selected rather than the non-NGSP certified value. For study baseline, if none of these preference HbA1c values are available at Visit 2, then Screening data will be used.

For standard descriptive tables of laboratory parameters by visit, in case of multiple measurements within a post-baseline time window for a visit, the worst value of these multiple measurements will be used for calculations.

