Table 6.3: 1 Patient sets analysed and treatment groupings (continued)

Class of endpoint	Patient sets					
	SCR	TS	TSactive	RS	mITT	PPS
Secondary efficacy endpoints						
Change in FPG [mg/dl] from baseline - ANCOVA					OC-AD-BOCF; OC (TG1)	
Change in body weight [kg] / SBP [mmHg] / DBP [mmHg] from baseline – MMRM					OC-AD; OC (TG1)	
Proportion of patients who achieve HbA1c goals < 6.5% and < 7.0%. Exact CI					NCF; OC (TG1)	

Table 6.3: 1 Patient sets analysed and treatment groupings (continued)

Class of endpoint	Patient sets					
	SCR	TS	TSactive	RS	mITT	PPS
Further safety endpoints						
Shift tables for the Tanner staging score from baseline		OC-AD (TG1, TG5)				
Descriptive statistics over time for growth velocity		OC-AD (TG1, TG5)				
Safety evaluation						
Overall summary of AEs		TG1, TG5, TG4	TG6			
Freq. of patients with the following AEs by treatment, SOC and PT 
 
• AEs
 
• AEs by worst intensity
 
• Drug-related AEs
 
• AEs leading to treatment discontinuation
 
• SAEs
 
• Other significant adverse events
 
• AESIs(except DKA and lower limb amputation)
 
		TG1, TG5, TG4	TG6			
Incidence rate of patients with AEs by treatment, SOC and PT		TG1, TG5				
List of patients with AESIs/other significant AE 
 
• DKA
 
• Events involving lower limb amputation
 
• Bone fracture
 
		TS				
Freq. of patients with other specific AE by treatment, SOC and PT: 
 
• Hypoglycaemic AE
 
• UTI (also investigator assessment, serious and leading to treatment discontinuation)
 
• Genital infection (also investigator assessment, serious and leading to treatment discontinuation)
 
• Acute pyelonephritis or urosepsis
 
• Volume depletion
 
• Ketone measurements
 
		TG1, TG4	TG6			

Table 6.3: 1 Patient sets analysed and treatment groupings (continued)

Class of endpoint	Patient sets					
	SCR	TS	TSactive	RS	mITT	PPS
Freq. of patients with other specific AE by treatment, SOC and PT: 
 
• Arthralgia
 
• Pemphigoid in bullous conditions)
 
		TG1	TG6			

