#### Observed cases - all data (OC-AD) analysis

All available data that were observed are considered. Any values taken after the start of rescue medication and any on- and post-treatment values will be kept.

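### SAP Table 6.7: 2 closes the Week 52 window on the last on-treatment day, so the post-treatment values that OC-AD keeps have no place at Week 52

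*SAP*

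**What the plan says.** Four parts of the SAP bear on this.

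- **Window.** In Section 6.7, Table 6.7: 2, the Week 52 / EoT row starts at Day 330 and ends at "Study drug stop date + X days". X depends on the endpoint and comes from Table 6.7: 1 (1 day for Tanner stage, 7 days for HbA1c). The text below the table adds: "The end of the time window of the last on-treatment visit (EoT) is endpoint dependent".
- **Post-treatment status.** Section 6.7 says: "Measurements taken after the last intake of study drug and end of the endpoint specific follow-up period will be considered post-treatment values". Section 6.1 agrees: the on-treatment period includes day stop + X, and the post-treatment period begins on the next day.
- **Visit assignment after stopping.** Footnote A, attached to the End column of Table 6.7: 2, says: "Post-treatment measurements will be assigned to visits in the same manner".
- **Data handling.** Section 6.6.1 defines OC-AD so that "Any values taken after the start of rescue medication and any on- and post-treatment values will be kept". Table 6.3: 1 lists "Shift tables for the Tanner staging score from baseline" and the growth velocity summaries as OC-AD for TG1 and TG5. TG5 runs from Day 1 to Week 52.

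**The concern.** The window's last day is also the last on-treatment day. A value cannot be both post-treatment and inside the Week 52 window, yet OC-AD exists to keep post-treatment values and footnote A says they are given a visit. A programmer who follows the table will drop them from Week 52. One who follows footnote A has no end date to use.

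What is at stake is follow-up after stopping. Protocol Sections 3.1 and 3.3.4.1 ask patients who stop drug to continue visits to study end, and Section 6.2.3 encourages them to undergo all procedures except PK sampling. In a paediatric trial, off-drug height and pubertal stage at one year belong in an all-data long-term table. The literal rule leaves them out even when they were collected.

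**Working it through.** **Inputs.**
- Planned days after randomisation (SAP Table 6.7: 2): Week 26 = 182, Week 42 = 294, Week 52 = 364.
- Window rule (SAP Section 6.7): a window closes at the midpoint between adjacent planned visits, and that midpoint day counts towards the earlier one. The same paragraph says windows are modified for endpoints with a different visit schedule.
- X (SAP Table 6.7: 1): Tanner stage 1 day. Height is not listed, so I take a range of 1 to 7 days as an assumption.
- Schedule (Protocol Flow Chart): Tanner stage at Visits 2, 5 and 8; height at Visits 1A, 5 and 8.

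**Step 1: reproduce the table's Day 330.** Midpoint of Weeks 42 and 52: (294 + 364)/2 = 329. Week 42 ends on Day 329 and Week 52 starts on Day 330, as printed.

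**Step 2: the start for Tanner stage and height.** After baseline these are measured only at Visits 5 and 8. The midpoint is (182 + 364)/2 = 273, so their Week 52 window starts on Day 274, not Day 330.

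**Step 3: the logical conflict.** For measurement day d and stop day s:
- in the Week 52 window: start ≤ d ≤ s + X
- post-treatment: d > s + X

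The two conditions exclude each other for every s, every X and every start day. Enumerating stop days 1 to 372 with X = 1, 7 and 30 on the Day 330 start found no post-treatment day inside the window.

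**Step 4: when the window is empty.** It is empty if s + X < start, that is, if s ≤ start − X − 1.

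| Case | Start | X | Empty for stops up to |
|---|---|---|---|
| Tanner stage | 274 | 1 | 274 − 1 − 1 = Day 272 |
| Height, X assumed 1 to 7 | 274 | 1 to 7 | Day 272 to Day 266 |
| Generic schedule | 330 | 1 | 330 − 1 − 1 = Day 328 |
| Generic schedule | 330 | 7 | 330 − 7 − 1 = Day 322 |

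**Step 5: two Tanner examples.**
- Stop on Day 120: the window runs from Day 274 to Day 121, so it is empty. A Visit 8 value on Day 365 has no visit.
- Stop on Day 340: the window runs from Day 274 to Day 341. An end-of-treatment value on Day 340 or 341 counts as Week 52; a Visit 8 value on Day 365 does not.

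**Step 6: contrast with other rows.** The Week 4, 12, 14, 30 and 42 windows end on fixed days. The Week 26 end depends on Day 141, Visit 5 drug intake, Day 210 and the Visit 6 date. None uses the stop date, so post-treatment values can be placed at those visits. Only Week 52 shuts them out.

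**The case against.** The strongest reply is that stop date + X was never meant to limit post-treatment values. Section 6.7 calls it the end for the last on-treatment visit and refers to the table that decides on-treatment status. Read with footnote A and OC-AD, the intent is that post-treatment values are assigned to visits. That is a plausible account of intent, and it stands as such. It does not supply a rule: footnote A points back to the same table, and no other Week 52 end is given.

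A reader might also infer more than the documents support:

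- *That the window is empty for everyone who stops early.* It is not. Patients who stop on Day 273 or later have a non-empty Tanner window, and an end-of-treatment value in it counts as Week 52.
- *That the long-term tables become completers-only.* Late stoppers contribute end-of-treatment values, and earlier visits are unaffected. The TG5 laboratory, lipid, renal, biomarker and vital-sign tables use OC-ROC, which excludes post-treatment data by design.
- *That the loss can be sized from adult discontinuation.* Protocol Table 7.7.1: 1 gives 8/206 = 3.9% to 16/152 = 10.5% by Week 18 or 24. Those are adult rates over a shorter period and would count every stopper, including those with a valid window. Protocol Sections 3.1 and 6.2.3 let early stoppers omit Tanner stage and height, and patients at Tanner stage V at Visit 2 are not reassessed.
- *That other Week 52 OC-AD tables are affected.* The further-endpoint sections are not in the public SAP, so this cannot be checked.

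**Conclusion.** The point holds as a contradiction within the SAP: read literally, Table 6.7: 2 admits no post-treatment value to Week 52, against footnote A and the OC-AD definition. That conclusion needs no numerical assumption.

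Its visible reach is two descriptive outputs up to Week 52, the Tanner shift tables and growth velocity. The Week 26 primary analysis has its own window end and is unaffected. OC and OC-ROC discard post-treatment values by definition, so they do not change.

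The Day 272 limit for Tanner stage assumes that the midpoint rule is applied to Visits 5 and 8 with X = 1; the corresponding limit for height rests on an assumed X. How many values would be lost is unknown. This is a minor point, worth correcting because the correction is nearly free.

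**What to change.** In SAP Table 6.7: 2, Week 52 / EoT row, state that stop date + X ends the window for on-treatment values only (OC and OC-ROC). For OC-AD, end it at the later of stop date + X and the actual Visit 8 date. Let Table 6.7: 1 decide only whether a value is on- or post-treatment.

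Do not add a fixed cap such as Day 372 (Day 365 plus the 7-day visit allowance). It would drop a late Visit 8, whereas other windows in the table are deliberately wider than the visit allowance.

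The footnote should also say whether the Section 6.7 preference for a value taken on the last day of treatment still applies at Week 52 under OC-AD. If it does, a patient with a Tanner value on stop Day 340 keeps that value rather than the Visit 8 one.

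Cost: one table cell and one footnote, with no change to data collection or to any confirmatory analysis.

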After the 26-week treatment period, all patients will enter a double-blind safety extension period up to 52 weeks. Patients who received placebo during the 26-week treatment period will be re-randomised to receive either linagliptin 5 mg or empagliflozin 10 mg or empagliflozin 25 mg. Since patients and investigators will stay blinded, investigators will have to perform an IRT call for all patients at Week 26 in order to get new trial medication kits assigned (see Section 4.1.4 for further details). The re-randomisation will be stratified by age at baseline (< 15 years; ≥ 15 and < 18 years) as described in [Section 7.6](#).

After the 52-week extension period, all patients will enter a 3-week follow-up period during which they will not be treated with study medication. The patient's participation is concluded when he has undergone the last planned visit (i.e. Trial Completion Visit); last-patient-last-visit-primary-endpoint will occur when all patients have completed 26 weeks of treatment. The end of the trial is defined as "last patient out" (i.e. last Trial Completion Visit completed by the last patient in the trial).

[figure not shown]
Except for patients who would discontinue the trial treatment for safety reasons, every effort should be made to re-introduce trial treatment after a temporary trial drug discontinuation. For the analysis of this trial it is very important that assessments for each planned visit are still performed in accordance with the [Flow Chart](#) even if patients discontinue trial treatment.

Patients who discontinue study drug prematurely should continue study visits until study end. Study assessments may be omitted if a patient is willing to return to the pre-defined study visits, with exception of blood drawing for safety lab tests, HbA1c and FPG, body weight, blood pressure and collection of adverse events and concomitant therapy. Refer to [Section 6.2.3](#) for premature discontinuation of treatment guidance.

Every attempt will be made by the investigator to ensure patients continue participating in the study during interruptions in trial drug intake and after permanent discontinuation of trial drug. The modified Intention-to-Treat (mITT) analysis requires that all trial patients be followed until study end even if the trial drug was temporarily interrupted or discontinued.

For a graphical presentation of the DINAMO™ trial and DINAMO™ Mono trial, see [Figure 3.1: 2](#) below.

a) DINAMO™

b. DINAMO™ Mono

[figure not shown]

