7.3.1.1.1 Analysis of the primary family of hypotheses

These confirmatory primary analyses will be performed using an effectiveness “wash-out” approach based on the mITT set with multiplicity adjustment for simultaneous testing of linagliptin and empagliflozin using the Hochberg-procedure. Patients will be assigned to the treatment they were randomised to at the initial randomisation, i.e. linagliptin 5 mg, pooled empagliflozin or placebo. HbA1c values measured after premature discontinuation of study drug or after rescue therapy was initiated will be included in the analyses. All available on- and off-treatment data up to the Week 26 time point will be included.

There will be different types of missing data to be considered for the imputation.

Table 7.3.1.1.1: 1 “Wash-out” approach – the missing data imputation method

Randomised treatment group: Placebo

Missing HbA1c data will be imputed for all scheduled visits up to Week 26, that includes Week 4, Week 12 and Week 26. Baseline will not be imputed.

Type of missing data	Data used for imputation	Method to use for	
		Non-monotone missing data	Monotone missing data
On- and off-treatment ⁴ data	Observed on- and off-treatment HbA1c data in the placebo group, including Baseline, Week 4, Week 12 and Week 26.	MCMC-MI ¹ (MAR ³)	SLR-MI ² (MAR ³)

Randomised treatment groups: linagliptin 5 mg and empagliflozin pooled.

Missing HbA1c data will be imputed for Week 26 only.

Type of missing data	Data used for imputation	Method
On-treatment data	Observed on-treatment HbA1c data in the respective treatment group, including Baseline and Week 26.	SLR-MI ² (MAR ³)
Off-treatment ⁴ data	Observed on- and off-treatment HbA1c data in the placebo group, including Baseline and Week 26.	SLR-MI ² (MNAR ⁵)

¹ Markov Chain Monte Carlo – Multiple imputation (MCMC-MI)

² Sequential linear regression – Multiple imputation (SLR-MI)

³ Missing at random (MAR)

⁴ Missing post-treatment data after permanent treatment discontinuation

⁵ Missing not at random (MNAR)

For the placebo group, missing HbA1c data, regardless on- or off-treatment, will be imputed for all scheduled visits up to Week 26.

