The effectiveness analyses will be performed on these imputed data sets plus the retrieved HbA1c data at Week 26 from the off-treatment patients, using an ANCOVA model with baseline HbA1c as a continuous model term, and with categorical terms for treatment and age. Rubin’s rules will be used to combine treatment estimates across the 500 completed imputations.

The implicit assumption underlying the imputations and analyses is that unobserved off-treatment patient measurements will lose any treatment effect immediately post-treatment discontinuation.

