### 7.4.3 HbA1c data summary

An overall summary for the availability of HbA1c [%] data at Week 26 will be presented by TG1 on mITT (OC-AD) set showing captured and missing Week 26 data and further classified as on- and off-treatment and within these categories further sub-classified as 'without prior rescue' and 'with prior rescue'.

Frequency of patients who completed, altered or missed the HbA1c [%] measurement at Week 26 will be tabulated by TG1 on mITT set to assess the impact of COVID-19.

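### For the Week 26 primary analysis, SAP 6.7 lets an HbA1c from the last treatment day displace a later off-treatment Week 26 value that the protocol says is analysed (rare and small; a minor wording fix)

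*SAP*

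**What the plan says.** SAP 6.7 allows one observation per time window. The default is the value closest to the planned day, which is Day 183 for Week 26. An exception follows for a value from the last treatment day: "this observation will be preferably selected over any later observation that is still within the time window". The next sentence brings the primary endpoint under it: "For the Week 26 primary analysis, this is applicable if study drug is stopped during the time window of the Week 26 visit". Footnote A of Table 6.7: 2 places early end-of-treatment (EoT) measurements in the same windows. For HbA1c, values are "considered on-treatment values if they have been obtained up to the end of the endpoint specific follow-up period", which Table 6.7: 1 sets at 7 days after the drug stop.

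The data definition for the confirmatory analysis points the other way:

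- Protocol 7.3.1.1.1: "HbA1c values measured after premature discontinuation of study drug or after rescue therapy was initiated will be included in the analyses". The ANCOVA is run on the imputed data sets "plus the retrieved HbA1c data at Week 26 from the off-treatment patients".
- Protocol 3.1: the mITT analysis "requires that all trial patients be followed until study end even if the trial drug was temporarily interrupted or discontinued".
- SAP 6.6.1, for the OC-AD data used in the primary analysis: "Any values taken after the start of rescue medication and any on- and post-treatment values will be kept".

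SAP 7.4.3 also plans a Week 26 availability table "showing captured and missing Week 26 data and further classified as on- and off-treatment".

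**The concern.** A preference for the last treatment day suits an on-treatment analysis (OC). It does not suit an analysis meant to use outcomes after discontinuation. Where it applies, a patient who stopped drug and came back, as the protocol asks, is analysed as if still on drug, with a value up to 42 days before the planned visit. The same data feed the secondary family (SAP 7.4.1.2). Observed placebo Week 26 values, selected by the same rule, are the basis for imputing missing off-treatment values in the active arms. The SAP 7.4.3 table would count the patient as captured on-treatment. SAP Section 4 does not list the rule as a change to the planned analysis.

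At stake is whether the selection rule for the primary endpoint agrees with the protocol's own data rule. The numerical effect is small.

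**Working it through.** **1. Which stopping days matter.** Let L be the last treatment day, with an HbA1c that day, and W the day of the later sample. The exception drops an off-treatment value that the default rule would keep when:

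- W − L ≥ 8 (past the 7-day limit, so off-treatment), and
- |L − 183| > |W − 183| (the later value is closer to the planned day).

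For Visit 5 on Day 183 and the tabulated window start of Day 141, this gives L = 141 to 175, or 35 days. For example, with L = 145 the default selects Day 183 (38 days off drug) and the exception selects Day 145. If Visit 5 falls anywhere in its ±7-day range, the count runs from 28 days (W = 176, L = 141 to 168) to 38 days (W = 186 or 187, L = 141 to 178).

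**2. Inputs for size.** From protocol 7.7.1: effect 0.55, SD 0.9, 50 per arm. SE = 0.9 × √(2/50) = 0.18. A t-test power calculation with these values at alpha 0.05 gives 85.7%, against the plan's 85%. Adult discontinuation counts come from Table 7.7.1: 1. The extremes are:

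- lowest: 8/206 = 3.88% over 24 weeks (168 days)
- highest: 16/152 = 10.53% over 18 weeks (126 days)

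**3. Assumptions.** Stopping is uniform over each adult trial's period at the adult rate. Every patient stopping on a decisive day has a last-day sample and returns. The documents support neither as a forecast, so the result is a ceiling on these rates.

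**4. Result on schedule.**

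| | Low | High |
|---|---|---|
| Share of an active arm | 3.88% × 35/168 = 0.81% | 10.53% × 35/126 = 2.92% |
| Patients of 50 | 0.40 | 1.46 |
| Shift, full loss of effect (share × 0.55) | 0.0044 | 0.0161 |
| In SE (÷ 0.18) | 0.025 | 0.089 |
| Shift, linear loss over 12 weeks | 0.0013 | 0.0048 |

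The last row uses protocol 3.2, which treats HbA1c as reflecting the preceding 12 weeks. Time off drug at Day 183 runs from 8 to 42 days, mean 25, so the mean loss is 25/84 = 0.298.

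**5. Sensitivity to the window start.** SAP 6.7 says windows are adapted to each endpoint's visit schedule, and HbA1c is not taken at Visit 4B. The midpoint of Weeks 12 and 26 is (84 + 182)/2 = 133, so the HbA1c window would start on Day 134. That gives 42 decisive days (134 to 175): 0.97% to 3.51% of an arm, and at most 0.0193 points (0.107 SE) with full loss.

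**6. Window ends.** On days after randomisation, the midpoint rule reproduces the ends of Week 4 ((28 + 84)/2 = 56), Week 12 (91), Week 14 (140) and Week 42 (329). For Week 30 it gives (210 + 294)/2 = 252; the table has 225. Visits 6 and 7, within their ±7-day limits, fall on Days 204 to 218 and 288 to 302, so neither lies in Days 226 to 252. The Week 26 end is set by its own formula, normally Day 210. That is 27 days past an on-schedule Visit 5 dose, and 13 to 34 days past it over the permitted visit dates.

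**The case against.** The strongest defence is that nothing is contradicted. The protocol and the OC-AD definition say which values are eligible. Only one value per window can be used, so any rule drops an eligible value, and a pre-specified tie-break is the technical detail a SAP exists to give. It is true that the protocol has no rule for choosing between two in-window values. That silence permits a tie-break, but it does not support one that systematically drops the retrieved off-treatment value the protocol says is analysed.

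Four further objections stand:

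- **The trigger is narrow.** No HbA1c visit is scheduled between Day 141 and Visit 5, and protocol 6.2.3 places the early EoT visit after the last intake. If that sample falls on a later day, the exception does not apply. Same-day dosing and sampling remains possible: patients are dosed in clinic on visit days (protocol 4.1.4), and the flow chart lists drug administration under Visit 8/EOT.
- **The direction is not established.** The rule applies in all arms. Rescue is allowed throughout and post-rescue values are included, so a later off-treatment value may be lower than the last-day one.
- **The window ends are alignment only.** Protocol 7.3 already censors data after the first extension dose for analyses up to Week 26, and the SAP rests on that section of the protocol.
- **Some text is missing.** SAP 7.4.1.3 and 9.4, the latter holding the technical description of the method, are not in the supplied text and may bear on value selection.

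**Conclusion.** The mismatch is real and minor. SAP 6.7 applies the last-day preference to the primary analysis by name, and in the case described it sets aside a value that the protocol's data rule is meant to use. With the tabulated window, at most about 0.8% to 2.9% of an active arm is affected. The shift is at most 0.016 points (0.09 SE) and more plausibly 0.001 to 0.005. These figures rest on adult discontinuation rates, uniform stopping, and a last-day sample and return for every such patient; the true number is probably lower. The shift favours active drug only if the effect wanes after stopping and rescue does not offset it.

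A reader might infer that the SAP turns the primary analysis into an on-treatment one, or that it materially inflates the drug effect. The documents do not support this. Off-treatment Week 26 values still enter whenever there is no last-day sample, and the ceiling above is a small fraction of a standard error. Nor do they support reading the late Week 26 window end as letting extension data into the primary result, given the censoring rule in protocol 7.3. The Week 30 discrepancy touches no in-window scheduled visit.

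**What to change.** In SAP 6.7:

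- Limit the last-treatment-day preference to on-treatment (OC) analyses.
- For the OC-AD primary analysis and the secondary family, select the HbA1c closest to Day 183 whatever the treatment status.
- Apply the laboratory preference order only between values of the same treatment status, as protocol 7.3 and SAP 6.7 already illustrate it. Applied first and across statuses, it could let an earlier on-treatment central value beat a later off-treatment local one and bring the problem back.
- Classify patients in the SAP 7.4.3 table by the value selected.

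For alignment only, cross-reference the protocol 7.3 censoring rule at the Week 26 window end, and reconcile the Week 30 end (Day 225) with the midpoint rule (Day 252) or state it as an exception. Neither is expected to change a primary result. Check SAP 7.4.1.3 and 9.4 for consistency.

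The cost is SAP wording and selection code before unblinding. No new data are needed.
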